13.6.2 Analysis secondary endpoint(s)

Pharmacokinetics of Procizumab (including AUC, C_{max} , terminal $t_{1/2}$, Cl, V) will be determined for each dose and overall. Changes over time in blood plasma levels and activity of cDPP3 and other variables (vital signs, laboratory parameters, ECG, angiotensin metabolites, cytokines) within each treatment group will be described and plotted. They may be analyzed exploratory (within or between groups) by repeated measures one- or two-way analysis of variance. Data will be log-transformed if necessary.

Differences between subjects will be analyzed using Chi² tests or Fisher exact tests for counts (e.g. adverse events). T-tests, Mann-Whitney-U tests, one- or two-way analyses of variance tests or Kruskal-Wallis tests will be implemented for continuous variables, with the choice of test depending on the number of groups compared, as well as the data's distribution.

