Different biomarkers/measurements associated with AK1967's pharmacodynamic activity (see the study protocol for a full overview) are measured at set intervals during the experimental protocol. DPP3 enzyme activity and concentrations measurements are also performed during each of the study's follow-up visits. All pharmacodynamic biomarker measurements represent single timepoint measurements, meaning no data transformation prior to analysis needs to be performed. DPP3 enzyme activity, concentration, adrenergic and renin-angiotensin system metabolite results will be analysed by descriptive summary statistics for the different scheduled determination time points as well as expressed as changes from baseline.

Data distribution for all pharmacodynamic biomarkers will be evaluated using the Kolmogorov-Smirnov test and normal/non-normal distribution will be reported. All variables will be expressed both as mean ± standard deviation (SD), as well as medians and interquartile ranges (IQR) in tables and graphical representations of the data. In case a value of one of these parameters is an outlier in a subject, this will be described separately. Between group differences in pharmacodynamic biomarkers will be assessed using one-way-RM-ANOVA tests (for normally distributed data), or Kruskal-Wallis tests (for non-normally distributed data). In case of a p-value of <0.05 for these tests (implying the presence of dosage groups with differences in a vital sign at a specific timepoint), subsequent Bonferroni or Mann-Whitney-U post-hoc tests will be performed (depending on data distribution), to assess which subgroups are different, and in what direction.

Form Valid From: 08/03/2024

Form Version: 1

Record Title: Clinical Statistical Analysis Plan CT-P1-001

Record Title:

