Data distribution for all pharmacodynamic biomarkers will be evaluated using the Kolmogorov-Smirnov test and normal/non-normal distribution will be reported. All variables will be expressed both as mean ± standard deviation (SD), as well as medians and interquartile ranges (IQR) in tables and graphical representations of the data. In case a value of one of these parameters is an outlier in a subject, this will be described separately. Between group differences in pharmacodynamic biomarkers will be assessed using one-way-RM-ANOVA tests (for normally distributed data), or Kruskal-Wallis tests (for non-normally distributed data). In case of a p-value of <0.05 for these tests (implying the presence of dosage groups with differences in a vital sign at a specific timepoint), subsequent Bonferroni or Mann-Whitney-U post-hoc tests will be performed (depending on data distribution), to assess which subgroups are different, and in what direction.

Form Valid From: 08/03/2024

Form Version: 1

Record Title: Clinical Statistical Analysis Plan CT-P1-001

Record Title:

Additional analyses related to the effects of AK1967 on safety endpoints

Between group differences in vital signs will be assessed using one-way-RM-ANOVA tests (for normally distributed data), or Kruskal-Wallis tests (for non-normally distributed data). In case of a p-value of <0.05 for these tests (implying the presence of dosage groups with differences in a vital sign at a specific timepoint, subsequent Bonferroni or Mann-Whitney-U post-hoc tests will be performed (depending on data distribution), to assess which subgroups are different, and in what direction.

Between group differences over time for vital signs, safety laboratory and inflammatory parameters (i.e. laboratory/inflammatory parameter changes during the course of the experimental protocol) will be analyzed using two-way-RM-ANOVA tests (for normally distributed data), or two-way-RM-ANOVA tests on ranked transformed data (for non-normally distributed data). Both tests will report the time*group interaction term to establish significance, which will be defined as p <0.05.

9 Contents of statistical tables and figures

	14 Tables and figures referred to but not included in the text	

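### SAP 8.6 and 8.7 name a one-way RM-ANOVA, which has no group term, for between-group comparisons of PD markers and vital signs, and leave the normality gate and the use of the pre-dose value open

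*SAP*

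**What the plan says.** SAP 8.6 (pharmacodynamic data analyses) states: "Between group differences in pharmacodynamic biomarkers will be assessed using one-way-RM-ANOVA tests (for normally distributed data". Otherwise Kruskal-Wallis is used. SAP 8.7 repeats the sentence for PD markers and adds: "Between group differences in vital signs will be assessed using one-way-RM-ANOVA tests", with the same alternative. In each place a parenthesis explains a significant result as "implying the presence of dosage groups with differences in a vital sign at a specific timepoint"; in 8.6 this stands in a paragraph about PD markers.

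The branch depends on normality: "Data distribution for all pharmacodynamic biomarkers will be evaluated using the Kolmogorov-Smirnov test". The SAP gives neither the version of that test nor the data to which it is applied.

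Baseline appears in the PD text only with the summaries: "results will be analysed by descriptive summary statistics for the different scheduled determination time points as well as expressed as changes from baseline". The SAP also says that PD measurements need no transformation before analysis.

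For vital signs, safety laboratory and inflammatory parameters, SAP 8.7 has a second test, a two-way RM-ANOVA on raw or ranked data: "Both tests will report the time*group interaction term to establish significance".

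Protocol 13.6.2 is more general. It allows, as an exploratory option, one- or two-way repeated-measures ANOVA within or between groups for cDPP3, angiotensin metabolites, cytokines, vital signs, laboratory values and ECG; adrenergic markers are not named. It adds that "one- or two-way analyses of variance tests or Kruskal-Wallis tests will be implemented for continuous variables" and that "Data will be log-transformed if necessary".

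**The concern.** A one-way repeated-measures ANOVA compares levels of a factor that every subject passes through. Here that factor can only be time, because each subject receives 3, 6 or 12 mg/kg or placebo once. The named model therefore cannot answer the question it is assigned.

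This matters most for DPP3, renin-angiotensin and adrenergic markers. For them it is the only parametric between-group test in the SAP, and they carry three of the secondary objectives. An analyst must guess the model, the form of the normality test and the tested quantity. Two analysts who both follow the SAP could then report different p-values.

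**Working it through.** The documents give no effect size, SD, correlation or power, so there is no planned figure to reproduce. The inputs they do give are four analysis groups of 6 (24 subjects), a two-sided 0.05 level (Protocol 13.1), and sampling at baseline, 2 h and 10 h for renin-angiotensin and adrenergic markers (SAP 5.2).

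**1. What the named model contains.** With 24 subjects and 3 times there are 72 values and 71 df. One-way RM-ANOVA splits them into time (2), subject (23) and error (46): 2 + 23 + 46 = 71. The only F test is time, on 2 and 46 df. The dose groups lie inside the subject term (23 = 3 between groups + 20 within) and are not tested. An ordinary between-group ANOVA at one timepoint tests groups on 3 and 20 df; ANCOVA with one covariate on 3 and 19.

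**2. Which markers have another between-group test in the SAP.**

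| Variables | One-way RM-ANOVA / Kruskal-Wallis | Two-way time*group |
|---|---|---|
| DPP3, renin-angiotensin, adrenergic | yes | no |
| Vital signs | yes | yes |
| Inflammatory parameters | yes, as PD biomarkers | yes |
| Safety laboratory | no | yes |

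**3. The normality gate.** For the plain test with estimated mean and SD, the largest D found at n = 6 comes from five equal values and one outlier. With values 0,0,0,0,0,1 the mean is 1/6 and the SD is √[(5/6)/5] = 0.408, so the five tied values lie at z = −0.408 and D = 5/6 − Φ(−0.408) = 0.833 − 0.342 = 0.492. The exact 5% critical value at n = 6 is 0.519 (p = 0.073 for D = 0.492). So the plain test applied per group of 6 never declares non-normality. Other readings do. The table shows how often data are called non-normal, for log-normal data with the fold effects of step 5.

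| Version and unit | log-SD 0.6 | log-SD 1.0 |
|---|---|---|
| Plain, any group of 6 | 0% | 0% |
| Lilliefors, any group of 6 | 44% | 70% |
| Plain, pooled n = 24 | 8% | 33% |
| Lilliefors, pooled n = 24 | 64% | 89% |

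Between the first and the last row, the p<0.05 result differs in 13% / 12% of data sets.

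**4. Post-dose value, change or ANCOVA, normal data.** Relative to the post-dose value, the error variance is 2(1−r) for change and 1−r² for ANCOVA. For assumed shifts of 0/0.5/1/1.5 SD, the noncentrality is 6 × (0.75² + 0.25² + 0.25² + 0.75²) = 6 × 1.25 = 7.5, divided by that factor.

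| r | Factors (post-dose / change / ANCOVA) | Power |
|---|---|---|
| 0.3 | 1 / 1.4 / 0.91 | 53% / 39% / 57% |
| 0.5 | 1 / 1.0 / 0.75 | 53% / 53% / 66% |
| 0.7 | 1 / 0.6 / 0.51 | 53% / 77% / 84% |

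Post-dose value and change swap rank as r crosses 0.5; ANCOVA is highest in each row.

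**5. Skewed markers.** Simulation with 20,000 runs, 6 per arm, overall test at 0.05, assumed fold effects 1/1.3/1.7/2.5 and r = 0.5:

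| Per-timepoint test | Power, log-SD 0.6 | Power, log-SD 1.0 |
|---|---|---|
| ANOVA, post-dose value | 44–45% | 13% |
| ANOVA, change | 53–54% | 14% |
| Kruskal-Wallis, post-dose value | 47–48% | 18% |
| ANOVA, log post-dose value | 54% | 22% |
| ANCOVA, log scale | 65% | 26% |

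ANOVA on the post-dose value and on the change agree on p<0.05 in about 75% / 88% of data sets; ANOVA and Kruskal-Wallis on the post-dose value agree in about 81% / 87%. At log-SD 0.3 the choice hardly matters: both quantities under both tests give the same answer in 98%. The type I error of log ANCOVA is 4.8–5.3%.

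**The case against.** The strongest reply is that this is a naming slip. The phrase about a specific timepoint, and the choice of Kruskal-Wallis as the alternative, both point to a between-group comparison at each timepoint. That stands. A reader might infer that the SAP will test time and report the result as a dose effect; the documents do not support this.

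A reader might also infer that the PD markers have no usable between-group test anywhere. That goes too far as well. Protocol 13.6.2 allows an exploratory two-way repeated-measures analysis between groups for cDPP3 and angiotensin metabolites. It is optional, does not name adrenergic markers, and is not carried into the SAP for any of these three marker families, so it does not settle the choice.

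Nor can it be said that the Kolmogorov-Smirnov test never rejects here. That holds only for the plain version applied per group of 6. ANOVA and Kruskal-Wallis are not a free choice either, since the gate selects between them; this is why agreement is given above in pairs.

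Finally, ANCOVA on the log scale goes further than the wording requires, and its gain depends on an assumed correlation. That is fair, and the minimum alternative below closes every proven ambiguity. But the pre-dose value is already collected, and the gain in step 4 does not depend on log-normality.

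**Conclusion.** The point holds. The model named in SAP 8.6 and 8.7 has no group term, and for DPP3, renin-angiotensin and adrenergic markers nothing else in the SAP gives a parametric between-group test. Deleting "RM" alone would not finish the job, because the version and unit of the gate and the tested quantity would still be open. These gaps follow from the text and need no assumption.

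Their size does need assumptions. The fold effects, log-SDs and correlations are illustrative, and the consequence is material at log-SD 0.6 to 1.0 but slight at 0.3.

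The reach is limited to secondary and exploratory p-values. Mean (SD) and median (IQR) are reported whichever branch is taken. The descriptive primary safety analysis and dose escalation are not affected. The SAP should be amended on this point.

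**What to change.** **Preferred.** In the PD paragraphs of SAP 8.6 and 8.7 and the vital-signs paragraph of 8.7, replace the one-way RM-ANOVA and the Kolmogorov-Smirnov gate with a between-subject comparison of the four groups at each scheduled post-dose timepoint. Specify it as ANCOVA adjusted for the pre-dose value, on the log scale for PD markers and untransformed for vital signs, and label it exploratory. Protocol 13.6.2 already permits log transformation; the SAP sentences saying that PD data need none must be aligned. The follow-up tests now hang on the normality branch, so they should be tied to the new model.

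**Minimum.** Delete "RM", state the version and unit of the Kolmogorov-Smirnov test, and state whether the post-dose value or the change is tested.

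**Cost.** Three SAP paragraphs and a little programming. If ANCOVA is seen as outside Protocol 13.6.2, Protocol 13.10 asks for a note to file. ANCOVA spends one degree of freedom, which costs 1–2 points of power if baseline is uninformative (at r = 0, 52% against 54% for log ANOVA at log-SD 0.6). The log scale costs 2–4 points if a PD marker is in fact normal with a CV of 20–30% (60–62% against 64% for untransformed ANCOVA at r = 0.5). The minimum alternative takes a few words and costs no power.

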8.7 Additional analyses

Pharmacodynamic data analyses (effects of AK1967 on DPP3 enzyme activity, concentration and renin-angiotensin metabolites)

- To determine the effects of AK1967 on DPP3 concentration (corrected and non-corrected) in healthy male volunteers.
- To determine the correlation between DPP3 concentration (corrected and non-corrected) and DPP3 activity.
- To determine the effects of AK1967 on renin-angiotensin system response measured in non-stabilized (equilibrium) plasma samples at day 7.
- To determine the effects of AK1967 on renin-angiotensin system metabolites measured in stabilized (protease inhibitor) and non-stabilized (equilibrium) plasma samples over all timepoints.
- To determine the correlation between renin-angiotensin system modulation measured in stabilized (protease inhibitor) and non-stabilized (equilibrium) plasma samples over all timepoints.
- To determine the correlation between DPP3 activity and renin-angiotensin modulation measured in stabilized (protease inhibitor) and non-stabilized (equilibrium) plasma samples.
- To determine the correlation between DPP3 concentration (corrected and non-corrected) and renin-angiotensin modulation measured in stabilized (protease inhibitor) and non-stabilized (equilibrium) plasma samples.

All pharmacodynamic biomarker measurements represent single timepoint measurements, meaning no data transformation prior to analysis needs to be performed. DPP3 enzyme activity, concentration (corrected and non-corrected values) and renin-angiotensin system metabolite (in stabilized and non-stabilized plasma) results will be analysed by descriptive summary statistics for the different scheduled determination time points, as well as expressed as changes from baseline. Correlations between pharmacodynamic parameters will be reported.

Data distribution for all pharmacodynamic biomarkers will be evaluated using the Kolmogorov-Smirnov test and normal/non-normal distribution will be reported. All variables will be expressed both as mean ± standard deviation (SD), as well as medians and interquartile ranges (IQR) in tables and graphical representations of the data. In case a value of one of these parameters is an outlier in a subject, this will be described separately. Between group differences in pharmacodynamic biomarkers will be assessed using one-way-RM-ANOVA tests (for normally distributed data), or Kruskal-Wallis tests (for non-normally distributed data). In case of a p-value of <0.05 for these tests (implying the presence of dosage groups with differences in a vital sign at a specific timepoint), subsequent Bonferroni or Mann-Whitney-U post-hoc tests will be performed (depending on data distribution), to assess which subgroups are different, and in what direction.

Form Valid From: 08/03/2024

Form Version: 1

Record Title: Clinical Statistical Analysis Plan CT-P1-001

Record Title:

Additional analyses related to the effects of AK1967 on safety endpoints

Between group differences in vital signs will be assessed using one-way-RM-ANOVA tests (for normally distributed data), or Kruskal-Wallis tests (for non-normally distributed data). In case of a p-value of <0.05 for these tests (implying the presence of dosage groups with differences in a vital sign at a specific timepoint, subsequent Bonferroni or Mann-Whitney-U post-hoc tests will be performed (depending on data distribution), to assess which subgroups are different, and in what direction.

Between group differences over time for vital signs, safety laboratory and inflammatory parameters (i.e. laboratory/inflammatory parameter changes during the course of the experimental protocol) will be analyzed using two-way-RM-ANOVA tests (for normally distributed data), or two-way-RM-ANOVA tests on ranked transformed data (for non-normally distributed data). Both tests will report the time*group interaction term to establish significance, which will be defined as p <0.05.

9 Contents of statistical tables and figures

	14 Tables and figures referred to but not included in the text	

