13. STATISTICAL ANALYSIS

13.1 Description of statistical methods

Parameters will be presented as mean ± SEM or median and interquartile ranges, depending on their distribution. Categorical data will be presented as counts and percentages. A two sided p-value <0.05 is considered significant. Statistical analyses will be performed with R (http://www.r-project.org). No interim analyses will be performed during the study protocol.

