13.9 Procedure for accounting for missing, unused and spurious data

Due to the small sample size spurious missing data will be imputed, if necessary, instead of deletion of the subject from the dataset. For continuous data, a missing value of a specific timepoint will be imputed by the mean of the value of the previous and next timepoint. If the last timepoint is missing,

Procizumab phase 1 study EU CT: 2023-507035-37-00 Radboudumc

the last observation is carried forward. If a subject drops out of the study prior to receiving study medication, this subject will be replaced, with a maximum of five replaced subjects. A newly recruited subject replacing a subject that dropped out will receive the treatment that was originally allocated for the subject they replace.

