8.2 Definitions, derived variables and handling of missing data

Definitions of time points / time windows

Baseline will be defined per parameter and will be the value/measurement at the following timepoints:

Parameter for	Timepoint
Demographics	Screening
Vital signs	Baseline (before IMP administration)
ECG	Baseline (Screening)
Local laboratory assessment	Baseline (before IMP administration)
Arterial blood gas analysis	Baseline (before IMP administration)

Filing: https://fourteenfour.dhcvisioncloud.com/dhcvision/document.jsp?key=DATABASE:1001;IO:1527897	Page 11 of 22
---	---------------

Form Valid From: 08/03/2024

Form Version:

Record Title:

Record Title: Clinical Statistical Analysis Plan CT-P1-001

Parameter for	Timepoint
Biomarker (DPP3 concentration and	Baseline (before IMP administration)
activity)	

Derived variables

Extent of exposure:

Extent of exposure will be defined as total exposure in mg and calculated as:

total exposure
$$[mg] = 20 \frac{mg}{ml} * IMP volume [ml] * factor$$

where IMP volume is the body weight adjusted IMP volume before addition of NaCl and factor equals 1 for treatment group 12 mg/kg AK1967, 1/2 for treatment group 6 mg/kg AK1967, and 1/4 for treatment group 3 mg/kg AK1967. Total exposure will not be calculated for the Placebo treatment group.

In case of premature termination of the infusion, total exposure will additionally be multiplied by $\frac{volume\ administered\ [ml]}{c}$ in order to account for only partly administration of study drug.

Exposure per kg body weight will be calculated as:

Exposure per kg body weight
$$\left[\frac{mg}{kg}\right] = \frac{total\ exposure\ [mg]}{body\ weight\ [kg]}$$

Body mass index (BMI):

$$BMI = \frac{Weight [kg]}{Height [m]^2}$$

Handling of missing values

Data from subjects who prematurely terminate the trial will be used to the maximum possible extent. Missing values will not be inputted.

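### Group-by-time differences are tested by repeated-measures ANOVA, which usually drops any subject with a gap, while the SAP withdraws the imputation that the protocol provided to avoid this

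*SAP*

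**What the plan says.** SAP 8.7, in the part on additional safety analyses, states that between-group differences over time in vital signs, safety laboratory and inflammatory parameters "will be analyzed using two-way-RM-ANOVA tests (for normally distributed data), or two-way-RM-ANOVA tests on ranked transformed data (for non-normally distributed data"). It continues: "Both tests will report the time*group interaction term to establish significance, which will be defined as p <0.05".

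SAP 8.2, on missing values, says: "Data from subjects who prematurely terminate the trial will be used to the maximum possible extent. Missing values will not be inputted". The last word is evidently meant as imputed. SAP 7.2 adds only a reference to a data review plan, which is not among the documents reviewed. Neither section says how an incomplete subject enters the repeated-measures test, and no mixed model is named.

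Protocol 13.9 gives the opposite rule and its reason: "Due to the small sample size spurious missing data will be imputed, if necessary, instead of deletion of the subject from the dataset". The method follows: "For continuous data, a missing value of a specific timepoint will be imputed by the mean of the value of the previous and next timepoint". A missing final value is replaced by the one before it. Protocol 10.2 does not replace men who discontinue after dosing.

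**The concern.** The usual two-way repeated-measures ANOVA works on a full subject-by-time grid. If one cell is empty and nothing is imputed, the subject leaves the test together with every value he did provide. The protocol foresaw this and imputed to keep subjects in. The SAP removes the imputation without acknowledging the change and keeps the test.

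At stake are groups of 6 (three doses and pooled placebo). Losing one or two men per group leaves the interaction tests less able to show a dose-related change in a safety parameter, and a non-significant result could then be read as reassurance. The two documents also lead to different subjects in the same test, a choice that should not remain open once data are seen.

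**Working it through.** **1. Inputs.** There are 24 subjects, 6 per AK1967 dose and 6 on placebo (SAP section 3). Protocol Table 8, without screening, gives these haematology and biochemistry times: baseline, 0.5, 1, 2, 4, 6, 10 and 24 h, which is 8 points; then 48 h and days 3, 7, 14, 21 and 28, which makes 14. Neither document gives a missing-data rate, so 1, 2 and 5% per sample, independent, are assumed.

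**2. Which points enter.** A parenthesis in SAP 8.7 ties the laboratory and inflammatory changes to the experimental protocol period. SAP 8.5 and 8.6 mention that period and the follow-up visits as two separate things. This favours the 8-point reading, but 8.7 lists no time points, so both are shown.

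**3. Expected subjects lost** = 24 × [1 − (1 − m)^T], for missing rate m and T time points:

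| m | T = 8: share complete | Lost of 24 | T = 14: share complete | Lost of 24 |
|---|---|---|---|---|
| 1% | 0.99^8 = 0.923 | 1.9 | 0.99^14 = 0.869 | 3.2 |
| 2% | 0.98^8 = 0.851 | 3.6 | 0.98^14 = 0.754 | 5.9 |
| 5% | 0.95^8 = 0.663 | 8.1 | 0.95^14 = 0.488 | 12.3 |

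At 1% missing, the chance that all 24 men are complete is 0.99^(8 × 24) = 0.145 with 8 points and 0.99^(14 × 24) = 0.034 with 14.

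**4. What one gap costs.** On a simulated 24 × 14 grid with one value removed, 335 values remain. A standard classical repeated-measures routine stopped because the data were unbalanced. Dropping the subject leaves 23 × 14 = 322 values, so 13 observed values are discarded. The interaction degrees of freedom fall from (3 × 13, 20 × 13) = (39, 260) to (39, 19 × 13) = (39, 247). A mixed model fitted to the same data used all 335 values from all 24 subjects.

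**5. Early stop.** A man who leaves after 48 h has given 9 haematology samples. With 14 points all 9 are lost to the test. With 8 points he is complete and loses nothing.

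**6. Effect on the interaction test (14 points, simulated).** Assumptions: random-intercept SD 1, residual SD 1, and a shift rising linearly with dose to 1.2 SD at the top dose at 5 of the 14 points; 2,000 runs per setting. Power with complete data was 0.42 to 0.43. With complete cases only, it was 0.36, 0.30 and 0.15 at 1, 2 and 5% missing. At 5%, about 7% of runs left too few subjects to test and count as non-significant. The false-positive rate with complete cases was 0.054, 0.048 and 0.047. The 8-point version was not simulated.

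**The case against.** The strongest reply is that the SAP is under-specified here rather than self-contradictory. It names R but no function, so fitting the repeated-measures design as a mixed model is not excluded. A reader might infer that the named test cannot meet the SAP's own policy. The documents do not support that. The promise in 8.2 concerns only men who terminate early, not a single lost sample, and the descriptive analyses in 8.5 honour it by listing and summarising whatever was observed. For an isolated gap, only the no-imputation rule bears on the test.

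A reader might also infer that the test selects men without problems. That requires follow-up visits to enter and unwell men to miss them. If only the treatment day enters, the samples come from one supervised stay and this mechanism largely disappears. Nor is there evidence of excess false positives from deletion when values are missing at random.

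Three further points stand. These are additional analyses beside a descriptive primary, and dose escalation rests on DSMB review. Independent missingness is pessimistic, because gaps that cluster within a man affect fewer men at the same overall rate. And if Protocol 13.9 governed, isolated gaps with a value on either side would be filled. None of this tells the analyst what to do with an incomplete subject, and on imputation the two documents give opposite answers.

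**Conclusion.** The concern holds as a limited one. Run in its usual form, the test in SAP 8.7 drops incomplete subjects, and the SAP has withdrawn the protocol's means of preventing this. The expected loss ranges from 1.9 to 8.1 of 24 subjects on the treatment-day reading and from 3.2 to 12.3 on the day-28 reading, for assumed independent missing rates of 1 to 5%. If no values are missing, there is no loss. Under random missingness the cost is information: simulated power of 0.36 instead of 0.43 at 1% missing over 14 points, under the assumed effect. The primary descriptive safety analysis and the escalation decisions are unaffected. A change is worthwhile because a method that keeps every observed value is available at little cost.

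**What to change.** In SAP 8.7, replace both repeated-measures ANOVA branches with a linear mixed model fitted by REML to all observed values, with Kenward-Roger degrees of freedom and terms for group, time and group-by-time, on the log scale where data are skewed. Specify in advance:

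- **Covariance.** Use a parsimonious structure, such as a random intercept with AR(1) or spatial-power errors; spatial-power suits the unequal spacing. An unstructured matrix over 14 times needs 14 × 15 / 2 = 105 parameters, too many for 24 men. Name an R routine that offers Kenward-Roger for the structure chosen.
- **Baseline.** Use it either as a response or as a covariate, not both, and say what happens if it is missing. As a covariate, it removes any man without a pre-dose value.
- **Time points.** List those that enter each test, for vital signs as well as laboratory and inflammatory parameters.
- **Reporting.** Give the numbers of subjects and values analysed per test.
- **Missing-data rule.** Reconcile SAP 8.2 with Protocol 13.9. The mixed model needs no imputation; if the SAP rule stands, record the departure as Protocol 13.10 provides.

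The one-way repeated-measures tests in SAP 8.6 and 8.7 need the same clarification. If the ANOVA is kept, the minimum is to state the complete-case rule and report the numbers analysed.

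The cost is SAP wording, with R already named in 8.1 and no new data. The small downside is that a covariance structure must be chosen in advance. The model does not cure missingness that depends on unobserved values.
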